#### 5. Specific Aims:

The primary objective will be to compare the incidence of adductor spasm (also known as the obturator reflex) during transurethral resection of posterolateral bladder tumors under general anesthesia.

Secondary objectives will include assessments of leg weakness and fall risks, as measured using a handheld dynamometer and the timed up and go (TUG) test, respectively. Adverse events related to the anesthetic and surgical techniques will also be recorded.

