#### Inclusion criteria

1. Patients  $\geq$  18 years of age undergoing TURBT for unilateral or bilateral posterolateral bladder tumors
2. Ability to understand and provide informed consent

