#### Methods:

Research related procedures: Veterans (n=60) will be randomized to the obturator block or neuromuscular block arm upon enrollment, using randomized permuted blocks of six (GraphPad Software, Inc). The TUG test and dynamometer measurements will be obtained preoperatively and one hour postoperatively. Handheld dynamometers are commonly used to determine leg muscle strength and have been utilized in multiple recent nerve block studies and other clinical settings [7, 8, 15]. The TUG test requires the participant to stand from a seated position, walk ten feet, turn around, and return to a seated position. The test is free and available to all health care

providers (<http://www.cdc.gov/steady/index.html>). It is a sensitive and specific tool for evaluating fall risk with excellent intra- and interrater reliability [16]. It is easily performed, does not require specialized equipment or training, and correlates well with other balance and gait measures [17]. Times  $\geq 13.5$  seconds are associated with an increased risk of falls [16, 17].

Once a potential study candidate provides consent to participate in the study, s/he will undergo a baseline TUG test and dynamometer measurements.

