#### Planned statistical analyses

All analyses will be conducted in JMP Pro 12.0 (SAS Institute, Cary, NC). Categorical measures (e.g. block success) will be summarized as percentages (%). For continuous measures (e.g. TUG, dynamometer), normally distributed measures will be summarized as means and standard deviations, and non-normally distributed measures will be summarized as median with interquartile range. Differences in block success between groups will be examined with  $\chi^2$  tests. Differences in dynamometer measurements and TUG tests will be examined through t-tests, with transformation of outcomes as necessary to satisfy assumptions of the statistical test.  $P < 0.05$  will be considered statistically significant.

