#### Sample size justification

The target sample size for the proposed study is  $n=60$  ( $n=30$  per group). Power calculations were performed assuming 80% power and  $\alpha=0.05$ . With  $n=60$ , our sample can detect a minimum 28% decrease in block success in the neuromuscular block group compared to the obturator block group, assuming a 97% success rate in the obturator block group. This sample size will also be able to detect a minimum group mean difference of 7.4 on the TUG ( $SD=10.0$ ).

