#### Obturator block group

Standard of care: After the induction of general anesthesia, the block will be performed on the side of the posterolateral bladder tumor(s). If a patient has bilateral posterolateral bladder tumors, bilateral blocks will be performed. A time out procedure will be performed confirming the patient's identity, the proposed surgical procedure, and laterality of the tumor(s) and block procedure(s). The patient's inguinal region will be cleansed with Chlorohexidine prep solution. A 21ga Pajunk SonoPlex needle will be advanced under ultrasound guidance and 20-30mL of 2% mepivacaine will be injected using an interfascial approach. All nerve blocks will be performed by [name], who has expertise in ultrasound-guided regional anesthesia. Block time will be counted as the time from needle insertion until the completion of the injections. Any inadequate/failed blocks will be recorded. Unless clinically indicated, neuromuscular blocking agents will be avoided (with the exception of succinylcholine for tracheal intubation).

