#### Neuromuscular block group

Standard of care: After the induction of general anesthesia, rocuronium (a neuromuscular blocking agent) will be administered intravenously in 5-10mg increments

titrated to a goal of 2/4 twitches. An obturator block will not be performed unless adductor spasm persists despite the administration of additional rocuronium.

Research related procedure: The incidence of block- and procedure-related adverse events, including the obturator reflex, will be recorded. In addition to clinical observation, a Nerve Integrity Monitor (Medtronic) will be used to detect adductor spasm using continuous electromyography. Adhesive skin (non-needle) electrodes will be placed on the thigh to objectively detect and record instances of adductor spasm.

Standard of care: Unless contraindicated, all patients will be extubated and transported to the post anesthesia care unit (PACU). The patients will then be discharged home or to a hospital room (per the surgical service).

Research related procedure: One hour after arrival to PACU or when discharge criteria are met (whichever comes first), repeat dynamometer measurements and TUG tests will be performed. Patients will be called 24-48 hours post procedure to inquire about falls or evidence of nerve injury, as well as patient satisfaction.

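### Neither the randomisation nor the analysis uses tumour laterality, although it sets how many legs are blocked in the obturator arm: a modest weakness that is cheap to repair

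*Combined protocol and SAP*

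**What the plan says.** All references are to the combined protocol and SAP, Section 6 (Research Plan) unless stated.

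- **Inclusion criteria** admit patients "undergoing TURBT for unilateral or bilateral posterolateral bladder tumors". Laterality is therefore part of the eligibility description.
- **Methods** randomises 60 patients at enrolment, "using randomized permuted blocks of six (GraphPad Software, Inc". No stratification factor is named. That there is a single list is inferred from this silence; it is not stated.
- **Obturator block group**: the block is given on the tumour side, and "If a patient has bilateral posterolateral bladder tumors, bilateral blocks will be performed". Side is confirmed at the time-out.
- **Neuromuscular block group**: intravenous rocuronium is "titrated to a goal of 2/4 twitches", and no step depends on side. An obturator block is possible there only as a fallback for persistent spasm.
- **Specific Aims** (Section 5): "The primary objective will be to compare the incidence of adductor spasm". Leg weakness and fall risk are secondary objectives.
- **Planned statistical analyses**: "Differences in block success between groups will be examined with" chi-square tests. "Differences in dynamometer measurements and TUG tests will be examined through t-tests". There is no laterality stratum, covariate or subgroup.

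The plan does not say whether a bilateral patient contributes one outcome or two, or which leg the dynamometer measures.

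**The concern.** Laterality is more than a convenient baseline covariate here. In one arm it determines how much treatment is delivered: one blocked leg or two. In the other arm it changes nothing about the treatment. The abstract says that the obturator block weakens the adductors and that its effect on fall risk is unknown, which is the question the TUG and strength measurements are meant to answer. A single obturator-arm mean that pools one-leg and two-leg blocks in an unspecified ratio answers it only for whatever mix happens to be enrolled.

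For spasm, it is a reasonable inference, though not a stated fact, that resection on both sides exposes two nerves. With 30 patients per arm, the number of bilateral patients on each side is left to chance, although the variable is in hand when allocation takes place.

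**Working it through.** **1. The plan's own figure.** "Power calculations were performed assuming 80% power" with alpha 0.05 (two-sided assumed), 97% success and a 28% decrease. The pooled two-proportion formula is n per arm = [1.96·√(2p̄q̄) + 0.8416·√(p₁q₁ + p₂q₂)]² / (p₁ − p₂)².
- Absolute reading, 97% v 69%: (1.041 + 0.415)² / 0.28² = 27.04, so 28 per arm. Power at 30 per arm is 84.1%.
- Relative reading, 97% v 69.84%: 28.2, so 29 per arm. Power at 30 per arm is 82.5%.
- TUG: a t-test with 30 per arm and SD 10.0 detects 7.36 with 80% power, against the stated 7.4.

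The sample size of 60 is reproduced, and nothing below changes it.

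**2. Chance imbalance.** Sixty patients were allocated by simulation in blocks of six. The bilateral share is assumed.

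| Bilateral share | One list: gap of 5 or more bilateral patients | Two lists: largest possible gap |
|---|---|---|
| 15% | about 10% of trials | 3 |
| 25% | about 18% | 3 |
| 40% | about 24% | 3 |

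With two lists, a gap of exactly 3 occurs in about 2% of trials.

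**3. What a gap of 5 does to spasm.** Assume that each leg carries risks of 31% (neuromuscular) and 3% (obturator), independently. The risks for a bilateral patient are 1 − 0.69² = 52.4% and 1 − 0.97² = 5.9%. A gap of 5 puts one arm 2.5 above the average count and the other 2.5 below. The difference moves by (2.5/30)(0.524 − 0.31) + (2.5/30)(0.059 − 0.03) = 0.018 + 0.002, about 2 percentage points, against a planned 28.

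**4. Error rates for spasm (simulated, one list, 10–40% bilateral).** With 31% per leg in both arms, the plain chi-square rejects in 4.8–4.9% of all trials. In trials with a gap of 5 or more it rejects in 5.7–6.0%, where the laterality-stratified test gives 5.0–5.1%. With 3% v 31% per leg, power is 92–96% for chi-square and 90–96% for the stratified test.

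**5. TUG.** Let a one-leg block slow patients by e seconds and, as an assumption, a two-leg block by 2e. The pooled arm difference is e(1 + q), where q is the bilateral share. For e = 7.4 it is 7.4 × 1.15 = 8.51, 7.4 × 1.25 = 9.25 and 7.4 × 1.40 = 10.36 at shares of 15%, 25% and 40%. None of these is the one-leg effect (7.4) or the two-leg effect (14.8).

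**6. Precision of separate results.** At 25% bilateral there are about 7.5 bilateral and 22.5 unilateral patients per arm. With SD 10, the standard errors of the arm difference are 10·√(2/7.5) = 5.2 s and 10·√(2/22.5) = 3.0 s.

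**7. Cost in overall balance.** With two lists and 60 patients in total, both lists can stop three patients into a block, so the arms can differ by up to 6 (33:27). The difference exceeds 3 in about 4–5% of simulated trials.

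**The case against.** The strongest reply is that stratification and adjustment are optional. Blocked randomisation followed by chi-square and t-tests is unbiased and holds its error rate, and a 2-point shift that needs an uncommon imbalance is negligible against 28. Even the 2 points is generous: if 31% is the risk for the whole arm and 25% of patients are bilateral, the per-leg risk is nearer 26% (1.25 × 0.26 − 0.25 × 0.26² ≈ 0.31). At 97% success the obturator arm expects 0.03 × 30 = 0.9 failures, so a stratified test has little to work with. All of this stands, and it limits the point to one of modest value.

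A reader might infer that the design is invalid or the type I error inflated. The documents do not support that: the excess appears only within the imbalanced trials, and the overall rate stays just under 5%.

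A reader might also infer that adjusting TUG for laterality would save a useful number of patients. That holds only if bilateral disease slows patients in both arms. The treatment descriptions put the second weakened leg in the obturator arm, apart from fallback blocks. On that mechanism, with 25% bilateral, simulated adjustment is worth about 0 patients at an assumed 5 s of extra slowing and about 1.4 at 10 s.

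What the reply does not answer is interpretation. Without a prespecified use of laterality, the pooled TUG and strength means cannot be separated except post hoc.

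**Conclusion.** The point holds as a cheap improvement of modest value. No stratification factor is named and no planned analysis uses laterality, although it sets the extent of treatment in one arm. The consequences are an avoidable chance of a notable imbalance (about 10–24% of trials) and secondary results that blend two different exposures. The effect on the primary comparison is small, validity is intact, and little or no power is to be gained.

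The size rests on assumed bilateral shares of 15–40%, on assumed independent per-leg risks, and on reading the silence in Methods as a single list. Supplying the expected bilateral share would settle most of this.

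**What to change.** - **Methods:** use separate permuted-block lists for unilateral and bilateral disease.
- **Planned statistical analyses, spasm:** define the outcome per patient. If randomisation is stratified, use a laterality-stratified Mantel-Haenszel test and risk difference. If enrolment has already begun on one list, leave allocation alone, keep chi-square as the primary test and give the stratified result as supportive.
- **Planned statistical analyses, TUG and strength:** include laterality and a laterality-by-arm term, and report the arm difference separately for unilateral and bilateral patients. A main effect alone is not enough, because the extra weakness is expected in one arm. Present the separate results as estimates with confidence intervals, since the bilateral stratum will be small.
- **Data collection:** record the side of every spasm, and state which leg or legs the dynamometer measures.

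The cost is a second list, one or two model terms, and the possible difference in overall arm sizes shown above. No extra patients are needed.

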#### Planned statistical analyses

All analyses will be conducted in JMP Pro 12.0 (SAS Institute, Cary, NC). Categorical measures (e.g. block success) will be summarized as percentages (%). For continuous measures (e.g. TUG, dynamometer), normally distributed measures will be summarized as means and standard deviations, and non-normally distributed measures will be summarized as median with interquartile range. Differences in block success between groups will be examined with  $\chi^2$  tests. Differences in dynamometer measurements and TUG tests will be examined through t-tests, with transformation of outcomes as necessary to satisfy assumptions of the statistical test.  $P < 0.05$  will be considered statistically significant.

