#### 4. Background:

Much of the available data on obturator blocks is taken from the orthopedic anesthesia literature on patients undergoing knee surgery. To date, there are no complications (including falls) related to obturator blocks reported in the literature. ONB is performed in patients undergoing TURBT to minimize or ablate the obturator reflex [2-4].

Ultrasound guided regional anesthetic techniques have a long record of safety and efficacy, and are commonly performed for patients undergoing surgery in both the outpatient and inpatient setting.

Neuromuscular blocking medications are commonly used to prevent patient movement under general anesthesia. Use of neuromuscular agents may result in postoperative weakness, which may lead to hypoxemia and airway obstruction, complaints of muscle weakness or fatigue, longer postanesthesia care unit stays, delays in tracheal extubation, increased risk of pulmonary aspiration, and atelectasis [11]. Additionally, adductor spasm has been reported despite the use of these medications [12, 13].

Furthermore, there is a study that suggests that use of an obturator nerve block in patients undergoing TURBT may prolong time to cancer recurrence in patients with superficial bladder tumors [14]. The obturator block results in a decreased incidence of adductor spasm, which allows for optimal surgical conditions and improved tumor resection [14]. The incidence of adductor spasm during TURBTs is currently unknown. While one study has estimated the incidence to be 16.5% [18], three others have reported it to be 40-55% [13, 19, 20] in patients with posterolateral bladder tumors.

Given the presence of the adverse events associated with use of neuromuscular blocking agents and the current lack of adverse events reported with the obturator block, we are interested in conducting an investigation comparing the two approaches in a prospective and randomized manner.

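### Does testing and powering an undefined block success, instead of adductor spasm, leave the primary comparison unsettled?

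*Combined protocol and SAP*

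**What the plan says.** Section 5 (Specific Aims) states: "The primary objective will be to compare the incidence of adductor spasm (also known as the obturator reflex". The Planned statistical analyses section does not name spasm. It says "Differences in block success between groups will be examined with" chi-square tests and otherwise mentions only the Timed Up and Go (TUG) and dynamometer results. The Sample size justification uses the same term: with 60 patients, "our sample can detect a minimum 28% decrease in block success in the neuromuscular block group compared to the obturator block group". The reference rate behind that figure is worded this way: "assuming a 97% success rate in the obturator block group". Block success is defined nowhere. The nearest text, under Obturator block group, asks for inadequate or failed blocks to be recorded and gives no criterion.

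Detection is described under Neuromuscular block group: "In addition to clinical observation, a Nerve Integrity Monitor (Medtronic) will be used to detect adductor spasm using continuous electromyography". The next sentence there, on the electrodes, reads: "Adhesive skin (non-needle) electrodes will be placed on the thigh to objectively detect and record instances of adductor spasm". No amplitude, timing or muscle is given, and no rule covers an EMG signal without visible adduction. In that arm rocuronium is "titrated to a goal of 2/4 twitches". In the obturator arm such agents are avoided, except succinylcholine for intubation or where clinically indicated.

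**The concern.** A primary objective should be the variable that is tested and powered. Here the objective uses one name and the test and power statement another, and nothing links them. If block success meant technical success of the injection, the stated power would not apply to spasm.

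The scoring of spasm also looks open. EMG may pick up activity that nobody sees, and only one arm is assigned maintained neuromuscular blockade. The Background says "Neuromuscular blocking medications are commonly used to prevent patient movement under general anesthesia", so thigh activity unrelated to the obturator reflex might be suppressed in that arm and recorded in the other. Conversely, a partly blocked reflex might show on EMG alone in the neuromuscular arm. With 30 patients per arm, the classification of two or three of them could decide significance. A scoring rule chosen after the data are seen would be open to challenge.

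**Working it through.** **1. Which reading fits the text?** The power statement compares block success in the neuromuscular group with block success in the obturator group.
- Technical success of a nerve block has no evident counterpart for rocuronium titrated to a twitch count, so a 69% technical rate in that arm has no clear meaning.
- Freedom from spasm has the same meaning in both arms and is the complement of the stated objective.

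**2. Does the stated sample size reproduce on that reading?** Inputs from the Sample size justification: success 0.97 and 0.97 − 0.28 = 0.69, 30 per arm, alpha 0.05 (taken as two-sided, which the plan does not state), power 80%. As spasm rates these are 3% and 31%. The test is the same whichever way the outcome is coded.

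Pooled formula: n = [1.96·√(2·p̄·q̄) + 0.842·√(p1q1 + p2q2)]² / d²
- p̄ = 0.83, so √(2 × 0.83 × 0.17) = 0.531
- √(0.97 × 0.03 + 0.69 × 0.31) = √0.243 = 0.493
- n = (1.041 + 0.415)² / 0.28² = 2.120 / 0.0784 = 27.04, so 28 per arm
- Power at 30 per arm: z = (0.28 × √30 − 1.041) / 0.493 = 1.00, giving 84.1%
- Exact enumeration at 30 per arm: 0.90 for Pearson chi-square, 0.78 for Fisher

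The planned 30 per arm is consistent with its stated 80%.

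**3. How sensitive is the result to EMG-only patients?** Expected spasm counts are 30 × 0.03 = 0.9 and 30 × 0.31 = 9.3, so about 1 v 9 (obturator v neuromuscular). With a and b spasms out of 30 and 30, Pearson X² = 60·[a(30−b) − b(30−a)]² / [30·30·(a+b)·(60−a−b)].

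| EMG-only patients added | Counts | X² | p |
|---|---|---|---|
| none | 1 v 9 | 7.68 | 0.006 |
| two, obturator arm | 3 v 9 | 3.75 | 0.053 |
| three, obturator arm | 4 v 9 | 2.45 | 0.117 |
| one in each arm | 2 v 10 | 6.67 | 0.010 |
| two, neuromuscular arm | 1 v 11 | 10.42 | 0.001 |

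At the design counts, of these cases only an excess in the obturator arm takes p across 0.05.

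**4. What would it do to power?** The documents give no EMG-only rate, so 5, 10 and 15 percentage points are assumptions. Exact Pearson power, starting from 0.90:

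| EMG-only events fall in | 5 points | 10 points | 15 points |
|---|---|---|---|
| obturator arm only | 0.64 | 0.39 | 0.21 |
| both arms equally | 0.78 | 0.71 | 0.65 |
| neuromuscular arm only | 0.95 | 0.98 | 0.99 |

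With equal rates in both arms, clinical-only and either-method scoring would disagree on significance in 16%, 24% and 30% of trials.

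**5. Do the other gaps close from the text?**
- *Sign of a spasm:* the Abstract describes adduction of the leg on stimulation of the obturator nerve, which supplies both trigger and clinical sign.
- *Any spasm or only persistent spasm:* further rocuronium, and then an obturator block, are allowed if spasm persists. The objective is incidence, and a spasm that later settles has still occurred.
- *EMG in one arm or both:* the text sits under the neuromuscular heading, but so do the transfer to recovery, the repeat TUG and dynamometer tests and the telephone call. The Methods give the TUG and dynamometer tests to all participants. The placement looks like a layout slip.

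**The case for a change.** The strongest contrary case is that, even with success read as no spasm, the outcome is not fully scorable. The plan records instances of EMG activity with no amplitude or timing, and no rule turns them into a yes or no per patient. The arms differ in exactly the drug that affects muscle activity. If true clinical spasm were 3% in both arms and 10% of the remaining patients in one arm had EMG-only events, the chi-square test would reject about 29% of the time. A written rule costs a few lines, while a rule chosen after results are seen cannot be repaired.

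Part of this stands. The EMG gap is real, and two patients can matter. But the asymmetry is inferred. No section says that unrelated thigh activity occurs during resection, and two opposite biases are equally plausible, so the net direction is unknown. The largest effects require every EMG-only event to fall in one arm at an assumed rate. The obvious remedy, one fixed amplitude for all patients with EMG-only events counted, would not cure the alleged bias. If partial blockade lowers muscle activity in one arm, a common threshold preserves that difference. Such a rule would be a preference and not a demonstrably better method.

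**Conclusion.** No change is called for. The wording is loose: the analysis and power statements use a term that is never defined and never tied to the named objective. This is a gap and not a contradiction. Freedom from spasm is the only reading that works in both arms, and under it the chi-square test addresses the primary objective and 30 per arm delivers about 84% power (pooled) or 0.90 (exact Pearson). Writing the definition down would record what the analysts would use anyway.

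What remains uncertain is the handling of EMG signals without visible adduction. Its possible size runs from negligible to decisive (p from 0.001 to 0.117 for two or three reclassified patients, starting from 1 v 9), but every such figure rests on assumed counts and an assumed arm. The conclusion assumes that the 97% is a spasm-free rate, that the test is two-sided, and that EMG is used in both arms. The first and third are the natural readings of the text, but neither is stated outright.

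### Does the comparison of block success need a named chi-square version and a stated scale for the 28% decrease?

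*Combined protocol and SAP*

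**What the plan says.** Under Planned statistical analyses, the whole rule for the binary outcome is that "Differences in block success between groups will be examined with" chi-square tests, at a 0.05 significance level. The section mentions no continuity correction, no rule for small cells and no sidedness.

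The Sample size justification sets 30 patients per group, 80% power and alpha 0.05, and takes 97% success for obturator patients. It states that "our sample can detect a minimum 28% decrease in block success in the neuromuscular block group compared to the obturator block group". It names neither the test behind that statement nor the scale of the 28%. The same section adds: "This sample size will also be able to detect a minimum group mean difference of 7.4 on the TUG", with an SD of 10.0.

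**The concern.** Three common tests fit the words chi-square: uncorrected Pearson, continuity-corrected and likelihood-ratio. In large samples they agree. Here the assumed 97% success implies only 30 × 0.03 = 0.9 failures in the obturator arm, and at such counts they can differ. This appears to be the only test that serves the primary objective in Specific Aims (incidence of adductor spasm). If the version were chosen after the data were seen, a borderline result could be called significant or not at will.

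The 28% is a second open point: 97% could fall to 69% (absolute) or to 69.84% (relative). The word minimum also looks inexact, because the smallest detectable drop depends on the test.

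**Working it through.** **Inputs.** From the Sample size justification: 30 per arm, 97% success under obturator block (failure rate 0.03), a 28% decrease, alpha 0.05, 80% power. Assumptions: two-sided testing and no dropout.

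**Sidedness.** It is not stated but can be inferred. With 30 per arm, SD 10 and 80% power, a t-test detects 7.36 on the TUG two-sided and 6.50 one-sided. The stated 7.4 matches the two-sided value.

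**Scale.** Absolute: 97 − 28 = 69%, failure rate 0.31. Relative: 0.97 × 0.72 = 69.84%, failure rate 0.3016.

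**The plan's own figure, Pearson by formula.** With p̄ the mean failure rate and d the difference,

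power = Φ{(d − 1.96·√[2p̄(1−p̄)/n]) / √[(p₁(1−p₁) + p₂(1−p₂))/n]}.

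- Absolute: p̄ = 0.17, null SE = √(2 × 0.17 × 0.83/30) = 0.0970, alternative SE = √((0.0291 + 0.2139)/30) = 0.0900. The standardised value is (0.28 − 0.1901)/0.0900 = 0.999, so power is 84.1%.
- Relative: p̄ = 0.1658, SEs 0.0960 and 0.0894, d = 0.2716. The standardised value is (0.2716 − 0.1882)/0.0894 = 0.933, so power is 82.5%.

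Solved for n at 80% power, the same formula gives 28 per arm (absolute) or 29 (relative). The stated 30 covers both.

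**Exact power.** All 31 × 31 possible tables were enumerated with binomial weights and a two-sided 0.05 threshold.

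| Test | 97% vs 69% | 97% vs 69.84% | Peak type I error |
|---|---|---|---|
| Pearson, uncorrected | 89.9% | 88.6% | 5.5% |
| Likelihood-ratio | 90.9% | 89.7% | 8.9% |
| Continuity-corrected | 77.8% | 75.2% | 2.7% |
| Fisher exact | 77.8% | 75.2% | 2.7% |

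Peak type I error is taken over common failure rates from 0.001 to 0.50. At 30 per arm the corrected and Fisher tests reject exactly the same tables.

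**Smallest detectable drop at 80% power, in percentage points.** Pearson 26.0 by formula and 23.0 exact; likelihood-ratio 22.3 exact; corrected or Fisher 28.8 exact. The stated 28 is not an overclaim for Pearson. It is marginally short for a corrected or Fisher test.

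**Where verdicts differ.** Failures, obturator vs neuromuscular:

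| Failures | Pearson p | Corrected p | Likelihood-ratio p |
|---|---|---|---|
| 0 vs 4 | 0.038 | 0.121 | 0.016 |
| 0 vs 5 | 0.020 | 0.062 | 0.007 |
| 1 vs 7 | 0.023 | 0.058 | 0.016 |
| 2 vs 8 | 0.038 | 0.083 | 0.032 |
| 1 vs 9 | 0.006 | 0.015 | 0.003 |

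The last row is close to the expected result (0.9 vs 9.3 failures), and there all three agree.

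At 97% vs 69%, at least two versions disagree in 13.1% of trials. Pearson and the corrected test differ in 12.2%, Pearson and likelihood-ratio in 1.0%. The smallest expected cell count falls below 5 in 40.8% of trials.

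**The case for a change.** The case for a change is that the omission touches what appears to be the primary comparison, that filling it costs a few words, and that whether the 80% power claim holds depends on the missing word. In about four trials in ten the smallest expected count would be below 5. An analyst may then feel free to move to a corrected or exact test after seeing the table, and exact power would be 75% to 78%. The documents also contain no positive sign that Pearson was intended: the stated 28 points lies nearer the corrected or exact minimum (28.8) than the Pearson minimum (26.0 or 23.0).

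The arithmetic in this case is correct. What remains of it is a condition on the sample size statement, not a fault in the plan. Nearly all the disagreement (12.2 of the 13.1 percentage points) comes from the continuity-corrected version, which the plan nowhere mentions. The Pearson test keeps its type I error close to nominal at these counts (5.5% at most), so a small expected cell does not in itself invalidate it.

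Two further arguments carry little weight. The spasm rates in Background (16.5%, and 40–55%) are not stated to apply under neuromuscular block, so they cannot show how often the versions would disagree here. The meaning of block success, which the plan does not define, is a separate question that naming a test would not settle.

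**Conclusion.** No change is called for; this is missing detail that an analyst fills sensibly. Read in the ordinary way, as an uncorrected Pearson test at two-sided 0.05, the plan meets its stated 80% power on either scale (84.1% or 82.5% by formula, 89.9% or 88.6% exact), with type I error of at most 5.5%. Absolute or relative makes a difference of 0.84 percentage points in the neuromuscular success rate and one patient per arm. Sidedness is settled by the TUG figure. The word minimum is loose but errs on the cautious side for Pearson.

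The conclusion rests on three assumptions: 97% success under obturator block, 30 evaluable patients per arm, and Pearson as the test applied. If a continuity-corrected or Fisher test were used, exact power would be 77.8% (absolute) or 75.2% (relative), short of 80% by 2 to 5 percentage points, so the adequacy of 60 patients is conditional on the test. Naming the test, labelling the scale or adding a confidence interval would be good practice, but would only record or supplement a comparison that is already sound as written.

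### The TUG and dynamometer comparisons do not name the quantity tested and ignore the measured baseline; ANCOVA would settle the choice and is generally more precise

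*Combined protocol and SAP*

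**What the plan says.** Under Methods, the two outcomes are measured twice: "The TUG test and dynamometer measurements will be obtained preoperatively and one hour postoperatively". The same section confirms that each consenting patient "will undergo a baseline TUG test and dynamometer measurements". The research procedures listed under Neuromuscular block group return to this after surgery, when "repeat dynamometer measurements and TUG tests will be performed".

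The whole analysis for these outcomes, under Planned statistical analyses, is: "Differences in dynamometer measurements and TUG tests will be examined through t-tests", with the outcomes transformed where the test's assumptions call for it. No baseline term appears, and the tested quantity is not defined as either the postoperative value or the change.

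Sample size justification does not resolve it: "This sample size will also be able to detect a minimum group mean difference of 7.4 on the TUG", with an SD of 10.0 that could belong to a single measurement or to a pre-post change. No other section defines a change score or an adjusted model.

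Both outcomes are secondary. Section 5 (Specific Aims) states: "Secondary objectives will include assessments of leg weakness and fall risks, as measured using a handheld dynamometer and the timed up and go (TUG) test".

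**The concern.** A pre-post design with two arms allows three ordinary comparisons: a t-test on the postoperative value, a t-test on the change, and a linear model for the postoperative value with the preoperative value as covariate (ANCOVA). All three target the same mean difference under randomization, but their precision differs and depends on the pre-post correlation r. With equal pre and post SDs, the change t-test is weaker than the postoperative t-test when r is below 0.5 and stronger when r is above 0.5. As written, the plan permits either t-test, and the 80% power given for a 7.4-second difference applies only to the one whose SD is 10.0.

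The secondary questions about leg weakness and fall risk rest on these comparisons, with 60 patients. Leaving the quantity unnamed also leaves room to settle it after the data are seen. Nothing suggests that this is intended, but naming the quantity in advance removes the possibility.

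**Working it through.** **Inputs from the documents.** 30 per arm, 80% power, alpha 0.05, TUG SD 10.0 and detectable difference 7.4 (Sample size justification); t-tests without a covariate (Planned statistical analyses).

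**Assumptions.** Two-sided testing (sidedness is not stated); r = 0.3, 0.5, 0.7, 0.8 (not given); equal pre and post SDs; normal outcomes on the scale of seconds.

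**Step 1: reproduce the plan's figure.** Two-sample t-test, 58 df. Power is the probability that a noncentral t with noncentrality d / (SD × √(2/30)) exceeds t(0.975; 58) = 2.002. For d = 7.4 and SD = 10 the noncentrality is 7.4 / (10 × 0.2582) = 2.866 and power is 80.5%. Power of 80% is reached at d = 7.36, which rounds to 7.4. The one-sided version gives 88.9% (normal approximation) and does not match. So 7.4 is the figure for an unadjusted two-sided t-test on whatever quantity has SD 10.0.

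**Step 2: SDs under each reading.**

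- Reading 1, SD 10.0 is one measurement: change SD = 10√(2(1−r)); ANCOVA residual SD = 10√(1−r²). At r = 0.7 these are 7.75 and 7.14.
- Reading 2, SD 10.0 is the change: single-measurement SD = 10/√(2(1−r)); ANCOVA residual SD = 10√((1+r)/2). At r = 0.7 these are 12.91 and 9.22.

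The detectable difference is 0.7356 × SD for the t-tests (58 df) and 0.7358 × SD for ANCOVA (57 df).

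**Step 3: results.** Each cell gives the detectable difference in seconds, then power at 7.4.

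| Reading | r | Postoperative t-test | Change t-test | ANCOVA |
|---|---|---|---|---|
| 1 | 0.3 | 7.36; 80% | 8.70; 66% | 7.02; 84% |
| 1 | 0.5 | 7.36; 80% | 7.36; 80% | 6.37; 90% |
| 1 | 0.7 | 7.36; 80% | 5.70; 95% | 5.25; 98% |
| 1 | 0.8 | 7.36; 80% | 4.65; 99% | 4.42; >99% |
| 2 | 0.3 | 6.22; 92% | 7.36; 80% | 5.93; 94% |
| 2 | 0.5 | 7.36; 80% | 7.36; 80% | 6.37; 90% |
| 2 | 0.7 | 9.50; 59% | 7.36; 80% | 6.78; 86% |
| 2 | 0.8 | 11.63; 43% | 7.36; 80% | 6.98; 84% |

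**Step 4: allow for estimating the baseline slope.** Multiplying the ANCOVA SD by √(1 + 1/56) raises its detectable differences by under 1%: 7.08, 6.43, 5.30, 4.45 (reading 1) and 5.99, 6.43, 6.84, 7.04 (reading 2). Simulation with 20,000 trials per setting and a true effect of 7.4 gives ANCOVA power of 83%, 90%, 97%, >99% and 93%, 90%, 85%, 84%, in line with the formula.

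**Step 5: where the gain disappears.**

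- At r = 0 under reading 1, ANCOVA has 80.4% power against 80.5% by formula, or 79.3% against 80.2% by simulation.
- With the postoperative SD at 10 and the preoperative SD at 5, the change SD is √(125 − 100r). The change t-test then detects 7.17, 6.37 and 5.46 at r = 0.3, 0.5, 0.7, against 7.08, 6.43 and 5.30 for slope-corrected ANCOVA. The two are within about 3% of each other. Both beat 7.36 for the postoperative t-test.

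**Step 6: the open choice.** Simulating no effect, 40,000 trials per r from 0.3 to 0.8, each t-test rejects about 5% of the time. Taking whichever of the two has the smaller p-value rejects about 9%. This is the worst case.

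No dynamometer figure is possible because the documents give no SD for it.

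**The case against.** The strongest reply is that the firm defect is one missing phrase, and that preferring ANCOVA to a valid t-test is a matter of efficiency on secondary endpoints. The primary outcome, adductor spasm, is untouched, and no figure in the plan is wrong. That stands, and it limits the weight of the point.

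The size of the gain is also uncertain. Equal SDs may not hold: the exclusion criteria narrow baseline mobility, while the repeat test follows general anesthesia, so a larger postoperative SD is plausible. A plain change t-test then recovers nearly all the gain. At low r the gain over the postoperative t-test nearly vanishes: slope-corrected ANCOVA power under reading 1 is 79.7%, 80.1% and 81.3% at r = 0, 0.1 and 0.2, against 80.5%. Reading 2 is the less natural reading of the sample size section, and the 43% and 59% figures also require a postoperative t-test to be run when change was planned for. Skewed TUG times may be transformed, in which case figures in seconds describe only roughly what is analysed.

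These points make the benefit variable, but they do not make ANCOVA a poor choice. In the cases examined it loses at most about 1% in detectable difference, while either t-test can lose much more, and which one does depends on an r that nobody can yet state.

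**Conclusion.** The concern holds. The plan measures a baseline, leaves it out of the model and does not say which quantity its t-tests compare. The consequence is lost precision and an unfixed secondary analysis; there is no bias, and the stated 7.4 is sound for an unadjusted test. For r between 0.3 and 0.8 with equal SDs, ANCOVA power at 7.4 seconds is 84% to above 99% if SD 10.0 is a single measurement, or 94% down to 84% if it is the change, against 80% for the t-test that matches the stated SD.

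Confidence is high on the omission and on the direction of the recommendation. It is lower on the size of the gain, which rests on an assumed r, on equal SDs and on untransformed data. The change is recommended because it costs almost nothing; it is not a condition for the trial's validity.

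**What to change.** In Planned statistical analyses, replace the t-test sentence for these outcomes with:

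> Postoperative TUG and dynamometer values will each be compared between arms by ANCOVA with terms for arm and the patient's own preoperative value. Where a transformation is needed, the same one is applied to both values. The adjusted difference will be reported with its 95% CI. An unadjusted t-test on the postoperative value is a sensitivity analysis.

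In Sample size justification, add whether SD 10.0 is the SD of a single TUG measurement or of the pre-post change.

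The cost is a few sentences in one section and a few words in the other. No visit, measurement or patient is added, and ANCOVA is a standard linear model.
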